3 OBJECTIVES AND ENDPOINTS

OBJECTIVES	ENDPOINTS	JUSTIFICATION FOR ENDPOINTS
Primary		
To evaluate screening completion (primary outcome) comparing interoperable, REDCap-based methods to EHR patient portal-based methods for delivering validated standard care anxiety and depression instruments to epilepsy clinic patients (Aim 1).	Screening completion – Yes or No	Proportion of screening instruments completed by each of the 4 methods prior to clinic visit will be used to compare the effect of the different methods on patient self-completion, and to estimate completion rates by different methods for use in future screening implementation trials.
Secondary		
To evaluate process measures comparing interoperable, REDCap-based methods to EHR patient portal-based methods for delivering validated anxiety and depression instruments to epilepsy clinic patients (Aim 1).	Research team time: -sending instruments -instrument data entry Participant time from instrument delivery to completion	This data will provide information to calculate staff resources needed to prepare for screener delivery and data entry in future studies. This data will provide additional potential information about whether the different screener delivery methods vary in promptness of patient response to screeners.
To evaluate accuracy of a reproducible approach to EHR and research system integration via Epic's Kitintegration with REDCap for Epic EHR flowsheet data, using flowsheet-stored anxiety and depression instruments from epilepsy clinics as a demonstration case (Aim2a).	Accuracy of Kit flowsheet REDCap plug-in data entry vs. manual data entry	This will provide key information about whether a Kit flowsheet REDCap plug-in enabled data collection may improve accuracy of EHR-based data collection compared to manual collection.
Tertiary/Exploratory		
To explore visit attendance among individuals who completed or did not complete anxiety and depression screeners (Aim 1). To explore research team time required to collect anxiety and	Clinic visit attendance: Visit completed vs. canceled vs. no-show	To explore for association between visit completion and screener completion for the different delivery methods.

OBJECTIVES	ENDPOINTS	JUSTIFICATION FOR ENDPOINTS
depression screener results from the EHR via Epic's Kit integration with REDCap for Epic EHR flowsheet data (Aim 2a).	Time for data collection (Kit vs. manual entry)	To explore potential research staff time savings resulting from data collection via Kit flowsheet integration with REDCap.

4 STUDY DESIGN

4.1 OVERALL DESIGN

Aim 1: In a randomized trial, to compare patient-completion success of REDCap- and EHR-based anxiety & depression instrument delivery methods (1-4, Figure 1).

In this randomized study of four modalities with N=220 individuals per arm and primary outcome proportion fully screened prior to clinic visit, we will compare Twilio text message delivery via REDCap vs. REDCap email survey links vs. EHR portal questionnaires with reminder message vs. current standard delivery EHR portal questionnaires without reminder (Figure 2). Screening instruments will be delivered by randomized method 7 days prior to scheduled clinic visit and outcomes occur by the time of the scheduled clinic visit. The study setting is the Wake Forest Comprehensive Epilepsy Center, with 2 clinic sites where adult patients are served (Atrium Health Wake Forest Baptist main campus, Atrium Health High Point Medical Center). EHR portal questionnaires without reminder is the current standard care screener delivery method.

Hypothesis: the screening completion proportion will vary across the 4 modalities tested.

[figure not shown]
Process measures will also be compared among the modalities.

Trial Phase: Non-FDA regulated pragmatic trial.

Aim 2a: To demonstrate Epic's Kit integration with REDCap for Epic EHR flowsheet data (anxiety & depression instrument test case in epilepsy). We will evaluate this approach by measuring accuracy and staff time for data collection via Kit flowsheet REDCap plug-in versus manual data collection.

[figure not shown]
Following build and testing, Kit Flowsheet REDCap plug-in will be launched in a production REDCap project and activated for double data entry of the flowsheet data generated via participant screener completion in the two EHR allocated arms of the randomized screening instrument delivery study (EHR with message and standard EHR). Entry #1 will be

Figure 1: Project Overview and Conceptual Model

Key: solid arrows: tools already active
open arrows: tools proposed to develop (thick border: full development; thin border: preparatory stages of development)

Pragmatic randomized study overview

manual and data entry #2 will be the REDCap Kit plug-in collected by a study team member without access to the manually collected data. A user who did not collect either the manual or Kit plug-in data (the reviewer) will review discrepancies between entries using a REDCap tool. **Accuracy** will be assessed by comparing Kit REDCap plug-in collected values to manually-collected values for the EHR-allocated visits. **Reproducibility/generalizability** of the Kit REDCap plug-in data collection method will be evaluated in a 2nd instance of Epic (Encompass) via use of the Kit flowsheet plug-in to pull the same anxiety and depression screening data from Encompass instance flowsheets (generated during clinical data conversion of the original WakeOne Epic instance based flowsheets to the new health system-wide Encompass Epic instance).

Exploratory sub-aim 2b: (this portion is NOT HUMAN SUBJECTS RESEARCH) To develop a governance process for integration of REDCap data into EHR discrete data fields via Epic AddFlowsheetValue API.

4.2 SCIENTIFIC RATIONALE FOR STUDY DESIGN

This project is designed to overcome key roadblocks to future research to close screening, action, and outcome gaps for anxiety and depression in epilepsy, specifically: 1. multi-site implementation-effectiveness trials to evaluate collaborative care in epilepsy, and 2. Implementation-focused trials to close the screening and treatment gap for anxiety and depression in epilepsy. This will be accomplished by developing tools that can be used flexibly to facilitate multi-site research while generating key preliminary data to estimate recruitment potential for collaborative care studies and evaluate potential impact of an instrument-delivery focused component of a refined, theory-informed implementation strategy for anxiety and depression screening.

Each of the 4 arms of the randomized trial represents a screener delivery method that could be used at sites in future trials and in routine clinical care, with the standard EHR arm representing the current standard practice at Wake Forest Comprehensive Epilepsy Center. This project will generate the preliminary data on screener completion for each modality to support options for screening and symptom measurement in future research that could be used flexibly at different sites in future implementation research. This project will also generate valuable quality improvement-related clinical data that could result in immediate change in practice for screener delivery in routine care to enhance care and improve performance on epilepsy quality measures.¹⁴

4.3 JUSTIFICATION FOR INTERVENTION

Patient completion of instruments. The patient-focused screening delivery methods are informed by a Capability, Opportunity, Motivation-Behavior (COM-B)-Behavior Change Wheel framework-informed implementation strategy model.⁶⁷ Patient-level barriers were identified and mapped to COM-B constructs (physical opportunity and automatic motivation), then intervention functions (enablement, environment restructuring), then a corresponding behavior change technique (prompts & cues).⁶⁷

The four instrument delivery methods to be used in this pragmatic trial represent distinct prompts & cues for screening instrument completion [1.text message, 2.customized email prompt, 3.generic EHR portal email prompt with customized EHR portal message after login to EHR portal, or 4.no message but presence of previsit questionnaires associated with a visit in the EHR portal]. Examining these multiple instrument delivery methods will generate outputs that will support flexibility in instrument delivery modalities across multiple sites in future multicenter studies in this area, as mentioned above.

These 4 distinct delivery methods are used to deliver identical standard care validated anxiety and depression screening instruments.

The specific wording and appearance of the instrument delivery methods will be further informed during study planning by input from five patient stakeholders (with whom the research team has a prior relationship) who will participate in a semi-structured interview on barriers and facilitators to pre-visit screening completion, informed by the COM-B-Behavior Change Wheel framework and will provide usability feedback on the screener delivery methods and reminder message wording. (Additional stakeholders may potentially be engaged, to provide five individuals the opportunity to participate in both feedback sessions).

4.4 END-OF-STUDY DEFINITION

The only participant interaction in this study is completion of the standard care anxiety/depression screeners prior to the epilepsy clinic visit after viewing the brief consent information. Delivery of screeners occurs 7 days prior to scheduled clinic visit and outcomes occur by the time of the clinic visit (instrument completion, visit completion). All data for Aim 1 is generated by completion of the epilepsy clinic encounter. Aim2a involves secondary data collection among some participants who completed EHR based screening instruments and thus will have consented for research use of the screener data.

The end of the study is defined as completion of all data collection for all participants as shown in the Schedule of Activities (SoA), **Section 1.3**.

5 STUDY POPULATION

5.1 INCLUSION CRITERIA

AIM 1: All visits scheduled at least 7 days in advance at two adult epilepsy-focused clinics of the Wake Forest Comprehensive Epilepsy Center will be included.

AIM 2a: All visits with completed anxiety and depression screening questionnaires from the EHR-allocated arms of the randomized study.

5.2 EXCLUSION CRITERIA

AIM 1: Age<18 years at baseline (7 days prior to the scheduled epilepsy clinic visit)

AIM 2a: no exclusions.

5.3 LIFESTYLE CONSIDERATIONS

N/A

5.4 SCREEN FAILURES

Individuals not included in the study due to age<18 years at one point in the study period who later meet inclusion criteria for a later visit (by attaining the age of 18 years prior to a later epilepsy clinic visit) may then be included.

5.5 STRATEGIES FOR RECRUITMENT AND RETENTION

Recruitment. Eligible patient visits will be identified via EHR clinic schedules. Baseline collection of the EHR-based existing clinical and demographic data will occur under a HIPAA waiver.

Due to the minimal risk classification for this study involving modified delivery methods for otherwise identical standard care screening instruments, a modified informed consent process is acceptable as outlined below.

Eligible participants will be randomized to method for delivery of pre-visit standard care screeners, and all screeners will be delivered with adherence to clinical communication and privacy policies, with an identical brief consent/information sheet prior to the screening questionnaires. The same wording will be used for all study arms to reduce the chance of group allocation bias that would undermine the research results:

- *Your epilepsy doctor has included questionnaires about your mood and anxiety as part of your clinic visit. Taking part in this survey may involve providing information that you consider confidential or private. Depending upon how you answer these questions, the responses may be shared with your neurology provider. Some information you provide may be used for research. Careful efforts will be made to keep your information confidential. You will not lose any services, benefits, or rights if you choose not to participate in this voluntary survey.*

This brief consent format is acceptable because the study is minimal risk (see section 2.3.3 for more information about the minimal risk classification).

Thereby, those who complete anxiety/depression screening instruments will provide consent for use of research data and potential epilepsy provider notification of passive suicidality screen if needed to minimize risk/enhance safety (see section 8.2 for details of safety plan).

For those who do not complete the anxiety/depression screeners, epilepsy provider notification is not applicable, and it is impractical to obtain informed consent:

- 1. It is impractical to approach individuals who canceled or missed the clinic visit.
- 2. For individuals who do not complete the anxiety/depression screeners but do attend the epilepsy clinic visit, it is impractical for appropriately trained staff to approach them for consent at the clinic visit, since these visits may occur at any time on any day, including simultaneously at disparate clinic sites.
- Thus, among those who do not complete the screening instruments, waiver of informed consent and HIPAA waiver are acceptable because the study is classified as minimal risk (see section 2.3.3 for more explanation of this) and because obtaining consent is impractical.

Our N=880 sample size compares favorably with the typical >1500 visits at Wake Forest Comprehensive Epilepsy Center adult clinics over 6 months, and with our experience during COVID-19-related volume disruptions, when 1097 visits were scheduled and 866 were completed over a 5-month period. Finally, based on our clinic data we expect only a modest decrease in numbers from visits to individuals, and we estimate 923 unique individuals will complete visits over 6 months and thus the sample size goal will be achieved within the 6-8 months of recruitment planned for this study.

6 STUDY INTERVENTION(S) OR EXPERIMENTAL MANIPULATION(S)

6.1 STUDY INTERVENTION(S) OR EXPERIMENTAL MANIPULATION(S) ADMINISTRATION

6.1.1 STUDY INTERVENTION OR EXPERIMENTAL MANIPULATION DESCRIPTION

While this is not a treatment study, below we describe the different methods of delivering standard care screening instruments that are examined in the study.

AIM 1: Methods to deliver screening instruments.

The anxiety and depression screening instruments are a best practice clinical and quality tool currently in use at the center without consent. The screener questions in the proposed research are identical to those in current clinical use, with the research involving only minor changes in the delivery method (while adhering to clinical communication policies).

The delivery methods are described below.

- Standard EHR: visit-attached instruments in patient portal available ≤7 days before visit (current practice)
- EHR with message: portal message encouraging completion sent and visit-attached instruments available ≤7 days prior (system sends generic email; specific portal message visible after patient login to EHR portal)
- REDCap survey: custom email with instrument link sent ≤7 days before visit encouraging completion
- Twilio® text via REDCap: secure text message delivery of questionnaires ≤7 days prior to visit

AIM 2a: THIS ONLY INVOLVES COLLECTION OF DATA FROM THE EHR for EHR-arm participants who completed the anxiety & depression instruments in the EHR, and thus consented for research use of this data.

There are no participant interactions.

The study methods for this secondary data collection and analysis are described below, but these methods do not constitute an intervention.

Implementation and evaluation of EHR/research database integration via Kit Flowsheet REDCap plug-in

Diverse patient data are stored in the Epic EHR as flowsheet rows built for clinical care or research as discrete data collection fields. In addition to custom data collection forms, flowsheets are how standard instruments are programmed into Epic including Promis® measures, GAD-7, NDDI-E and other validated patient-reported outcome measures. However, integrating flowsheet discrete data with other research systems such as REDCap is a roadblock to translational research, and Epic's flowsheet webservices enforce a 72-hour lockout timeframe due to potential performance risk. Therefore, the GetFlowsheetRows webservice is not feasible for research data collection occurring >72 hours after entry. Epic's Kit is a set of database views available in all Epic systems with Caboodle data warehouse implementation.⁶⁶ It is designed to perform large data extracts and analytical reporting in an accessible manner. Furthermore, it requires less training for developers and enables quicker runtimes and quicker report writing compared to the Clarity relational database.⁶⁶ Similar to Clarity, the data accessible by Kit could be 24 hours old, but there is no lockout time, which makes Kit ideal for research applications involving retrospective data extraction for analysis. Thus, Kit integration is more generalizable for REDCap research database integration than native Epic webservices approaches, and it overcomes the prior roadblocks our research team encountered with the GetFlowsheetRows webservice. In this aim, an experienced consultant computer scientist will collaborate with Drs. [name] and [name] to integrate REDCap API functionality with Epic's Kit Flowsheet API by developing a REDCap plug-in. As mentioned in preliminary data, the team has prior experience developing REDCap APIs and the necessary tools. Epic provides a sandbox development environment for all Kit APIs,⁶⁶ including the Flowsheets API to be integrated with REDCap. Akin to other Epic webservices including FHIR, Epic's App Orchard platform controls the allowed APIs and other respective authentication details. Atrium Health Wake Forest Baptist is equipped and licensed with the Kit functionality and is populating flowsheets now.

Kit Flowsheet API REDCap Integration & Data Collection. Following build and testing, the REDCap plugin for Kit Flowsheet integration will be launched in a production REDCap project and activated for data entry of the flowsheet data generated in the EHR allocated arms of the randomized instrument delivery study. Entry #1 will be manual and data entry #2 will be via the REDCap Kit flowsheet plugin by a user without concomitant access to the manual data entry fields. A user (the reviewer with rights to review discrepancies between entries and the source data) will use a REDCap instrument to review for discrepancies and reconcile discrepancies.

6.1.2 ADMINISTRATION AND/OR DOSING

REDCap anxiety and depression instruments (Generalized Anxiety Disorder-7, GAD-7 and Neurological Disorders Depression Inventory-Epilepsy, NDDI-E) currently in use by the PI will be adapted and enabled for Twilio text functionality and custom survey link email messages via REDCap developer services. EHR patient portal messages to encourage instrument completion will be prepared with support as needed by Epic analyst team, similar to the study team's prior work.

6.2 FIDELITY

6.2.1 INTERVENTIONIST TRAINING AND TRACKING

N/A.

6.3 MEASURES TO MINIMIZE BIAS: RANDOMIZATION AND BLINDING

Randomization and blinding. Visits will be randomized 1:1:1:1 to the 4 conditions using blocked randomization to reduce the chance of imbalances, and to help protect against temporal trends. Randomization will be stratified by presence of an existing antidepressant prescription. The randomization table will be prepared with consideration of our previously observed rates of antidepressant prescribing in our epilepsy clinic setting (152 of 536 consecutive screened individuals with epilepsy prescribed an antidepressant). Prior to the start of enrollment, the randomization table will be prepared by the study statistician and submitted to the REDCap developer to put into production. For each visit, the participant's baseline data collection will be completed; activation of the random assignment may then occur. Until that time, the assignment will be concealed to the PI and all other study team members to enhance ***rigor and reproducibility***. The nature of outcome collection prevents study team blinding to allocation for primary outcome ascertainment. Study team will enter instrument results obtained via REDCap into the EHR flowsheets prior to clinic visit (identical EHR location as with EHR allocation). Timely entry is feasible using REDCap email alerts to the study team (method used by PI in prior projects).

The brief consent will have identical wording for all delivery arms to minimize potential bias that could be introduced by the informed consent process related to the different study arm allocations (see sections 5.5 and 10.1.1.1 and 10.1.1.2).

6.4 STUDY INTERVENTION/EXPERIMENTAL MANIPULATION ADHERENCE

N/A

6.5 CONCOMITANT THERAPY

N/A

6.5.1 RESCUE THERAPY

N/A

7 STUDY INTERVENTION/EXPERIMENTAL MANIPULATION DISCONTINUATION AND PARTICIPANT DISCONTINUATION/WITHDRAWAL

7.1 DISCONTINUATION OF STUDY INTERVENTION/EXPERIMENTAL MANIPULATION

N/A as there are no ongoing study interactions/this is not a treatment study.

7.2 PARTICIPANT DISCONTINUATION/WITHDRAWAL FROM THE STUDY

N/A as the only participant interaction is a one-time completion of standard care screeners delivered by one of the allocated methods.

7.3 LOST TO FOLLOW-UP

N/A

8 STUDY ASSESSMENTS AND PROCEDURES

8.1 ENDPOINT AND OTHER NON-SAFETY ASSESSMENTS

Baseline demographics and clinical information (including whether there is evidence of an existing antidepressant prescription) will be collected from existing EHR based information using SMART on FHIR REDCap integration. These also include: sex, race, ethnicity, age, diagnoses, zip code, and prescriptions.

Anxiety and depression instruments.

Generalized anxiety disorder-7 (GAD-7)^{68,69} & Neurological Disorders Depression Inventory-Epilepsy (NDDI-E)^{70,71} are well-validated, freely available anxiety and depression instruments that satisfy the American Academy of Neurology Epilepsy Quality Measure for anxiety and depression screening at every visit¹⁴ and are National Institute of Neurological Disorders and Stroke(NINDS) Common Data Elements. Automated EHR-based procedures are already in place for these instruments to be attached as EHR-portal previsit questionnaires and available prior to a scheduled visit for all active adult epilepsy specialty providers at the Wake Forest Comprehensive Epilepsy Center.

AIM 1 Outcomes. Outcomes are determined by the scheduled clinic visit (Table 2), with primary outcome defined as instrument completion prior to visit date/start time. Technical reasons for lack of instrument completion (eg. no patient portal account, no email address available in EHR system, text messages cannot be sent via clinical protocols) will be recorded, but the primary analysis will follow intention to treat principles and include all randomized individuals.

Table 2: Aim 1 Outcomes

Outcome	Source	How obtained?
---------	--------	---------------

Instrument completion (primary)	EHR or REDCap (allocated method)	Review REDCap (REDCap arms) Manual EHR review (EHR arms)
Research team time: sending instruments	REDCap	Start stop timing fields REDCap (seconds)
Research team time: instrument entry (into EHR or REDCap, based on allocation)	REDCap	Start stop timing fields REDCap (seconds)
Patient time from instrument delivery to completion among screening completers	REDCap (and EHR if randomized to EHR)	Send time: study team-activated REDCap timing field at instrument delivery Completion time: review of instrument completion timestamp in EHR or REDCap
Clinic visit completion: visit completed, canceled or patient no-show?	EHR	Manual chart review

Baseline instrument completion proportion over a few month timeframe prior to pragmatic trial initiation may be collected via a CLARITY data pull to estimate pre-trial completion rate using the standard EHR method.

AIM 2a: Accuracy of Kit Flowsheet REDCap plug-in data entry will be assessed by comparing Kit REDCap plug-in-collected values to manually-collected values for the EHR-allocated visits, with review of original-source EHR entries to determine true values for all discrepancies identified

Staff time for data collection will be measured to the nearest second using REDCap timestamps as in Aim 1.

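### Primary-outcome ascertainment is unblinded and follows a different route in the REDCap and portal arms, with no full check of portal-arm visits recorded as not completed

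*Combined protocol and SAP*

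**What the plan says.** Section 8.1 has the "primary outcome defined as instrument completion prior to visit date/start time". Table 2 names the source as "EHR or REDCap (allocated method" and the method as a review of REDCap in the text and email arms and "Manual EHR review (EHR arms" in the two portal arms. For the secondary outcome of patient response time, the same table takes the completion time from "review of instrument completion timestamp in EHR or REDCap", so both systems date a completion.

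Section 6.3 adds: "The nature of outcome collection prevents study team blinding to allocation for primary outcome ascertainment". That sentence is not limited to the portal arms.

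Two other statements in Section 8.1 matter here. The portal forms are part of routine care: "Automated EHR-based procedures are already in place for these instruments to be attached as EHR-portal previsit questionnaires". Nothing says that this is switched off for patients allocated to text or email. Also, a pre-trial completion proportion "may be collected via a CLARITY data pull to estimate pre-trial completion rate using the standard EHR method".

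Three provisions bear on checking. Section 10.1.8 compares a sample of source data with the database. Section 5.1 limits Aim 2a, and so its double collection, to portal-arm visits with completed questionnaires. Section 3 justifies Aim 2a by asking whether the plug-in might be more accurate than manual collection from the EHR.

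**The concern.** Aim 1 compares REDCap-based with portal-based delivery, and the method of finding completions changes at exactly that line. The routes are also prompted differently. Sections 6.3 and 8.2 describe REDCap alerts to staff when a form is completed. For the portal arms, Section 8.2 describes alerts tied to NDDI-E results and critical values, and its summary covers positive suicidality screens. A general completion alert is not clearly described.

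If one route misses or misdates more completions than the other, the omnibus test can reject when the delivery methods perform equally well. The completion proportions, which are meant to inform later studies, would be off as well. The checks in place would not reliably expose this: a portal completion recorded as absent never enters Aim 2a, and the quality-control comparison covers a sample only.

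**Working it through.** **Inputs from the plan.** Four arms, 1:1:1:1 (Section 6.3). N = 220 per arm, overall chi-square test, alpha 0.05, true range 0.16, power at least 80% (Section 9.2). Four groups give 3 degrees of freedom and a critical value of 7.815.

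**Formula.** Noncentrality λ = n × Σ(p_i − p̄)² / [p̄(1 − p̄)]. The rejection probability is the upper tail of the noncentral chi-square with 3 df beyond 7.815.

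**The plan's own figure.** The least favourable pattern with range 0.16 is 0.42, 0.50, 0.50, 0.58. Then λ = 220 × (2 × 0.08²) / 0.25 = 2.816 / 0.25 = 11.264, and power is 81.4% (also 81.4% in 200,000 simulated trials). The claim of at least 80% holds.

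**Missed completions in one pair of arms.** No error rate or base completion rate is given, so both are assumed. Let all arms have true completion p, and let a share m of completions be missed in two arms, with perfect ascertainment in the other two. The observed proportions are p, p, p(1 − m), p(1 − m).

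Example with p = 0.50 and m = 0.05: the observed values are 0.50, 0.50, 0.475, 0.475; p̄ = 0.4875; Σ(p_i − p̄)² = 4 × 0.0125² = 0.000625; λ = 220 × 0.000625 / (0.4875 × 0.5125) = 0.550; rejection probability 0.0845.

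| True completion | Share missed | Spurious difference (points) | Missed per arm (220·p·m) | P(reject), nominal 0.05 |
|---|---|---|---|---|
| 30% | 2% | 0.6 | 1.3 | 0.0522 |
| 30% | 5% | 1.5 | 3.3 | 0.0644 |
| 30% | 10% | 3.0 | 6.6 | 0.1136 |
| 50% | 2% | 1.0 | 2.2 | 0.0552 |
| 50% | 5% | 2.5 | 5.5 | 0.0845 |
| 50% | 10% | 5.0 | 11.0 | 0.2089 |
| 70% | 2% | 1.4 | 3.1 | 0.0622 |
| 70% | 5% | 3.5 | 7.7 | 0.1335 |
| 70% | 10% | 7.0 | 15.4 | 0.4276 |

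**Direction.** The plan's text leaves at least three mechanisms open:

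- Staff overlook portal completions in the portal arms. This favours REDCap.
- Patients in the REDCap arms answer the routinely attached portal form and are not counted, because only the allocated system is read. For equal shares the probabilities are those in the table, but the difference favours the portal arms. The plan does not say whether such completions should count.
- Portal forms filed at or after visit start are counted as on time. If 2%, 5% or 10% of true non-completers in the portal arms are misclassified in this way, the rejection probability is 0.0622, 0.1335 or 0.4276 at 30% completion, 0.0552, 0.0845 or 0.2089 at 50%, and 0.0522, 0.0644 or 0.1136 at 70%. This also favours the portal arms.

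**The case against.** Completion before a set time is an objective fact. In every arm, staff read a record that the system has stored and dated, so knowing the allocation leaves little room for judgement. The team cannot realistically be blinded either: it sends the instruments, enters REDCap results into the EHR and receives arm-specific alerts. Section 6.3 is right about that, and a script would not change it. At a 2% miss rate the inflation is small, 5.2% to 6.2% across the completion rates shown. The larger figures need one completion in ten to be lost, all in one direction, and nothing in the documents points to that. Section 10.1.8 does provide some source checking. All of this stands. It limits the size of the point but does not supply the missing check on recorded non-completions.

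A reader might also infer that errors can arise only in the portal arms and must favour REDCap. The documents do not support this. Staff review both systems, both hold completion timestamps, misdating can go either way, and reading only the allocated system can lose portal completions by REDCap-arm patients.

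**Conclusion.** The point holds in a non-directional form. The ascertainment route differs by arm along the main contrast, it is unblinded, each route looks in one system only, and no full check of portal-arm non-completions is described. The net direction of any bias is unknown.

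Its size cannot be established from the documents. It is negligible if errors are near 2% and material if they reach 5% to 10% in one pair of arms. Those rates, the 30% to 70% completion range, error in one direction only and perfect ascertainment elsewhere are all assumptions. The calculation shows what the design is exposed to and is not evidence that bias will occur. The sample size statement is unaffected. This is an inexpensive improvement to the only primary endpoint.

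**What to change.** In Table 2 and the SAP:

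- Assign completion in all four arms by one programmed rule: both instruments (GAD-7 and NDDI-E) completed, with system timestamps before the scheduled visit start. Use REDCap timestamps and a Clarity extract of portal completion times.
- Run the rule on every randomized visit, including those recorded as not completed, and query both systems for every participant.
- State how completion by a non-allocated route is classified. Because staff enter REDCap results in the same EHR location (Section 6.3), the extract must separate patients' portal submissions from staff entries.
- Keep manual chart review to resolve mismatches.
- In Section 6.3, add that outcome status is assigned by the same programmed rule in every arm. It need not claim that the team is blinded.

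Clarity is preferable to the Kit plug-in here, because the plug-in's accuracy is itself an Aim 2a endpoint.

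The cost is wording plus programmer time for the extract and for matching rows to visits. Section 8.1 foresees a Clarity pull only as an option for a pre-trial proportion, so it must be confirmed that Clarity holds visit-level completion timestamps.
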